#### 1. Background and Purpose

Monocyte migration plays a key role in the pathogenesis of Rheumatoid arthritis (RA) since the number of monocyte derived macrophages is higher in RA synovial tissue compared to normal joints and is well correlated with radiological damage, joint pain and inflammation. However, the signaling pathway(s) responsible for enhanced recruitment of monocytes into the RA synovial joint space is unknown. To address this important issue, we performed microarray studies to identify differentially regulated genes in RA synovial fluid macrophages and identified IL-7 Receptor (IL-7R) as one of the most highly upregulated genes in RA synovial fluid macrophages. Our preliminary data shows that IL-7R expression is elevated 45 fold in RA synovial fluid and 10 fold in RA peripheral blood (PB) in vitro differentiated macrophages compared to normal PB macrophages by real-time RT-PCR and/or FACS analysis. Consistently, in RA synovial tissue, IL-7R is also elevated on macrophages in the lining and sublining compared to normal synovial tissue. We found that expression of IL-7R in RA PB monocytes and macrophages is modulated by TNF- $\alpha$  Interestingly, concentrations of IL-7R have a strong correlation with disease activity score as determined by 28 joint count (DAS28) and TNF-α levels in RA monocytes. Moreover, our preliminary data documents that IL-7 is secreted from TNF-a treated RA macrophages and can attract IL-7R+ monocytes from the circulation to the RA joint at concentrations of IL-7 detected in RA synovial fluid.

Based on our results we hypothesize that RA patients with a TNF- $\alpha$  driven active disease have elevated expression of IL-7/IL-7R and thereby response to anti-TNF- $\alpha$  therapy reduces IL-7-mediated monocyte migration and the number of IL-7R+macrophages in the RA joint. To test our hypotheses, in aim 1 we will examine whether expression of IL-7 or IL-7R in RA PB cells correlates with RA disease severity and response to anti-TNF- $\alpha$  treatment (Fig. 1). To date the contribution of IL-7 and IL-7R to RA pathogenesis and its role as a TNF- $\alpha$  responsive gene has not been described.

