#### 2. Protocol Methodology

**Detection of IL-7 and IL-7R expression levels in RA patients with active and inactive disease:** RA patients will be referred and informed written consent will be obtained by [name]. Blood samples will be collected from patients that have been diagnosed with RA based on ACR classification criteria. The study will include 200 donors. The total number of subjects are divided into two groups to yield a power of 95% at a type I error 5% level [determined based on the preliminary data]. In the first group, 200 donors will be treated with methotrexate, plaquenil and/or prednisone (DMARDs) that either achieve remission (DAS28<2.6) or do not achieve remission (DAS28<2.6). 50 donor will be utilized as they respond to DMARDs and achieve remission (DAS28<2.6) and 150 donors that do not respond to DMARDs will be transferred to second group. In the second group, 150 donors will be treated with methotrexate, plaquenil and/or prednisone and Cimzia® (provided to us by UCB).

In the first group of patients, blood samples will be obtained from RA patients treated with Disease modifying anti rheumatic drugs (DMARDs) such as methotrexate, plaquenil and/or prednisone that achieve remission (DAS28<2.6). The patients that achieve remission (DAS28<2.6), blood will only be taken once at the patients routine visit.

The second group will consist of RA patients that did not respond to "DMARDs". These patients will further receive (DMARDs) such as methotrexate, plaquenil and/or prednisone as well as Cimzia® (provided to us by UCB) free of charge. Cimzia® is a FDA approved drug and is a standard of care. Blood samples will be obtained from the patients treated with DMARDs including methotrexate, plaquenil, and/or prednisone and Cimzia® (provided to us by UCB) that have inactive remission (DAS28<2.6). In this group, blood samples will be collected onset of the study as well as 3 and 6 months after treatment with Cimzia at patient's visit through our collaboration with the aforementioned rheumatologists. Patients receiving intra-articular steroid injections will be excluded from the study.

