PB mononuclear cells will be isolated from RA whole blood and drawn into EDTA or CPT tubes and isolated by Histopaque gradient centrifugation. Monocytes will be isolated from RA PB mononuclear cells by negative selection (as shown in the preliminary data) and half of the monocytes will be differentiated to macrophages for 7 days. The expression levels for IL-7 and IL-7R will be determined by real-time RT-PCR and FACS analysis.

In our statistical analysis, we will first perform a stratified analysis to evaluate the differential expression levels in RA patients with active and inactive disease, controlling for the type of treatment. Data analysis will be performed in collaboration with an UIC Center for Clinical and Translational Science statistician. Specifically, we will perform the comparison of IL-7 and IL-7R expression among RA patients with active (DAS28>2.6) vs. inactive disease (DAS28<2.6) for DMARDs group (group 1). We will then perform a similar comparison for the DMARDs and Cimzia® therapy group (group 2). The stratified analysis can adjust for the potential confounding effect of treatment received and allows for the detection of the potential differential relationships between expression levels of IL-7 or IL-7R and disease status. We will also perform a pooled regression analysis in which the expression logarithm of IL-7 or IL-7R from patients is regressed on the treatment group indicator [DMARDs (group 1) versus on DMARDs plus Cimzia® therapy (group 2)] and disease status (active or inactive disease) which would demonstrate the interaction between treatment groups and disease activity. Such an analysis pools subjects from two treatment groups together and can therefore increase the sample size, and hence potentially the power of detecting the relationships between biomarkers and disease status. The RA samples will be collected over a 2 year period and the data will be analyzed in the last year of the proposal.

**Measure outcomes:** For any of the genes that demonstrate at least 2.5 fold increase (89% sensitivity calculated based on our preliminary data) in active disease compared to remission, correlation coefficient will be calculated for that gene expression level, rheumatoid factor, Cyclic Citrullinated Peptide Antibody (anti-CCP), C-Reactive Protein (CRP), DAS28 and disease duration.

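### The treatment-adjusted analyses use DAS28 only as active or inactive at 2.6; a continuous DAS28 term, free of the 2.5-fold gate, should be added beside that contrast

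*Combined protocol and SAP*

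**What the plan says.** Section 1 (Background and Purpose) raises two related questions. Its narrative says that aim 1 will examine whether expression in blood cells "correlates with RA disease severity and response to" anti-TNF treatment. The formal statement of Aim 1, later in the same section, is a comparison of patients above and below DAS28 2.6.

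Section 2 (Protocol Methodology) gives three analyses that use DAS28:

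- **Stratified comparison.** Expression is compared in "active (DAS28>2.6) vs. inactive disease (DAS28<2.6) for DMARDs group (group 1", and then: "We will then perform a similar comparison for the DMARDs and Cimzia® therapy group (group 2".
- **Pooled regression.** Log expression is regressed on treatment group and "disease status (active or inactive disease", and is meant to show their interaction.
- **Correlation, under Measure outcomes.** A "correlation coefficient will be calculated for that gene expression level, rheumatoid factor", anti-CCP, CRP, DAS28 and disease duration. It is limited to genes at least 2.5-fold higher in active disease than in remission, and no treatment adjustment is mentioned.

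**The concern.** The first two analyses are the ones that account for treatment, and both reduce DAS28 to one split. A patient just above 2.6 and a patient with very high activity are coded alike. So is a group 2 patient who improves a good deal by 3 or 6 months but stays above 2.6: that patient is active throughout, and the model cannot see the improvement.

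The one analysis that uses the score does not fill this gap. It has no stated treatment adjustment, and a gene with a steady gradient across DAS28 but less than a 2.5-fold difference at the split never reaches it.

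At stake is how precisely the study can estimate the treatment-adjusted relation between expression and severity. In one reading of the groups, what is at stake is whether that relation can be estimated at onset at all.

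**Working it through.** **The plan's own figures.** The plan gives no figure for this loss and no DAS28 distribution. Section 2 claims 95% power without an effect size or SD, so it cannot be checked. Section 10 claims 80% power for a paired t test with 200 subjects at effect size 1.25. The noncentral t gives more than 99.9%, so that figure is not reproduced, but this is a separate matter and does not bear on the point here.

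**Inputs.**
- Total size, section 2: "The study will include 200 donors".
- Split on DMARDs alone, section 2: "50 donor will be utilized as they respond to DMARDs and achieve remission (DAS28<2.6) and 150 donors that do not respond to DMARDs". This gives 50/200 = 25% inactive and 75% active.
- Preliminary association, section 1: R² = 0.56, so r = √0.56 = 0.748.
- Assumed, not in the documents: normal DAS28, a linear relation, one sample per patient, two-sided 5% test.

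**Step 1: information kept by the binary term, without treatment adjustment.** For a normal predictor cut at proportion p, the share kept is φ(z_p)² / [p(1 − p)].

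At p = 0.25, z = −0.674 and φ = 0.3178. The share is 0.3178² / 0.1875 = 0.539, a loss of 46%. A simulation gave 46.3%. Then 200 × 0.539 ≈ 108 effective patients, and a correlation shrinks by √0.539 = 0.734.

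| Inactive/active split (normal DAS28) | Loss |
|---|---|
| 50/50 | 36% |
| 40/60 | 38% |
| 30/70 | 42% |
| 25/75 | 46% |
| 20/80 | 51% |
| 10/90 | 66% |

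At 25/75 with other shapes, the loss is 44% (uniform), 52% (t with 5 df) and 60% (right-skewed gamma, shape 4). These are scenarios, not bounds.

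**Step 2: power without treatment adjustment, n = 200, 25/75.** Power = Φ(atanh(r)·√197 − 1.96), with r replaced by 0.734r for the binary term.

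| True r | Continuous | Binary |
|---|---|---|
| 0.20 | 81% | 55% |
| 0.25 | 95% | 74% |
| 0.30 | 99% | 88% |
| 0.748 (preliminary) | >99.9% | >99.9% |

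The smallest r detectable with 80% power is 0.20 continuous and 0.27 binary.

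**Step 3: with treatment group in the model.** What matters now is the split within each group, and section 2 does not settle who is in group 1. It first describes all 200 donors on DMARDs, then describes group 1 blood as one sample from each patient in remission. Group 2 is the non-responders, sampled at onset, 3 and 6 months.

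Suppose group 1 is the 50 remitters and group 2 the 150 non-responders. At onset every group 1 patient is inactive and every group 2 patient active. Status and group are then the same variable, so the adjusted binary effect cannot be estimated.

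Continuous DAS28 still varies within groups. Under the Step 1 assumptions, 1 − 0.539 = 0.461 of its variance remains after removing group. With a common slope, the squared partial correlation is 0.461r² / (0.461r² + 1 − r²), and power is Φ(atanh(partial r)·√196 − 1.96):

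- r = 0.20: partial r = 0.137, power 49%.
- r = 0.25: partial r = 0.173, power 69%.

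The continuous term is estimable, but with less power than the 81% and 95% in Step 2. The group 2 split at 3 and 6 months is not given, so the adjusted loss at those times cannot be calculated.

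**The case against.** Four points on the other side carry weight.

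- **Aim 1 is worded as active versus inactive.** The remission contrast answers it directly. A reader might infer that the 2.6 split is wrong or should give way to a slope. The documents do not support that: severity is a second question, in the background narrative, and calls for an added term. This point stands in full.
- **The 46% is not a property of the planned analyses.** A reader might take it as the information that the treatment-adjusted models throw away. It is an unadjusted figure for one split and one distribution. The 25/75 split fits only if group 1 is analysed as all 200 donors before transfer, and that comparison has no Cimzia contrast in it. This also stands.
- **Power may not suffer.** At the only association the documents report, R² = 0.56, both codings exceed 99.9%. A reader might infer that the study is underpowered because of the split, and the documents do not show that. The reassurance has limits, though. No treatment adjustment is stated for that R². If its p-values come from ordinary two-sided correlation tests, they imply only about 21 to 22 monocyte and 29 to 30 macrophage samples. No such value is reported for IL-7. An interaction is also usually estimated less precisely than a main effect.
- **The DAS28 score is already used.** The correlation under Measure outcomes does use it, so it would be wrong to say the plan ignores the score. The narrower complaint remains: that use is gated and has no stated treatment adjustment.

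**Conclusion.** The point holds in a limited form. Both treatment-adjusted analyses use DAS28 only as a split at 2.6, and this gives up precision on the severity question in section 1.

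For a normal DAS28 and a linear relation, the unadjusted loss is about 36% to 66% over splits from 50/50 to 10/90. The consequence for power depends on the true association: negligible near the preliminary R² of 0.56, material at correlations of about 0.2 to 0.3.

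The adjusted loss cannot be given as one number. It is total at onset if the groups are 50 remitters and 150 non-responders, and unknown at 3 and 6 months. In that onset case the continuous term rescues the estimate only if linearity holds. The two groups' DAS28 ranges do not overlap, so a curved relation could pass for an interaction with group.

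This is a worthwhile improvement to the analysis. It does not invalidate the remission contrast as an answer to Aim 1.

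**What to change.** Before the data are analysed, amend the statistical paragraph of section 2 as follows.

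- Beside the planned pooled model, fit one in which DAS28 at the time of the sample is a continuous term, with its treatment-group interaction.
- Fit it for both IL-7 and IL-7R, whether or not they pass the 2.5-fold gate.
- Keep the contrast at 2.6 as the answer to Aim 1. The remission definition does not change.
- State who is in group 1 for the analysis and which draws enter the model. If several draws per group 2 patient enter, allow for correlation within patient.
- Check linearity within each group, and report any onset interaction with the caution about non-overlapping ranges.

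The cost is one extra model, a linearity check, and keeping the numeric DAS28 at every draw. The documents imply that the score is available, since patients are classified by it and it is to be correlated with expression. They do not say that it is recorded at each sample, so the amendment should say so.

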IL-7R is the top gene identified in synovial fluid macrophages and its expression in monocytes ( $R^2=0.56$  and  $p=8.4x10^{-5}$ ) and macrophages ( $R^2=0.56$  and  $p=2.4x10^{-6}$ ) strongly correlates with RA disease activity suggesting that IL-7R may be a predictor for disease severity. Hence in this proposal, novel translational studies will be performed in order to determine whether IL-7R and IL-7 are RA signature genes for disease activity and if these genes are markedly reduced in anti-TNF- $\alpha$  therapy responders compared to nonresponders.

**Figure 1.** Specific aim is proposed to elucidate the significance of IL-7/IL-7R expression in peripheral blood cells to RA disease activity and response to anti-TNF- $\alpha$  treatment.

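### Correlations with DAS28, CRP, RF, anti-CCP and disease duration are calculated only for a gene that rises at least 2.5-fold in active disease, so a clearly correlated gene can end with no correlation reported

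*Combined protocol and SAP*

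**What the plan says.** Section 1 (Background and Purpose) states the question for aim 1 with no threshold: "we will examine whether expression of IL-7 or IL-7R in RA PB cells correlates with RA disease severity". It reports preliminary R² = 0.56 between IL-7R expression and disease activity, in monocytes and again in macrophages, and concludes that expression "strongly correlates with RA disease activity suggesting that IL-7R may be a predictor for disease severity".

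Section 2 (Protocol Methodology) plans three kinds of analysis:

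- A stratified comparison with disease status in two levels: "we will perform the comparison of IL-7 and IL-7R expression among RA patients with active (DAS28>2.6) vs. inactive disease (DAS28<2.6) for DMARDs group", then the same for group 2.
- A pooled regression of log expression on treatment group and "disease status (active or inactive disease) which would demonstrate the interaction between treatment groups and disease activity".
- Under Measure outcomes, the correlations: "correlation coefficient will be calculated for that gene expression level, rheumatoid factor, Cyclic Citrullinated Peptide Antibody (anti-CCP), C-Reactive Protein (CRP), DAS28 and disease duration". These are limited by the words that open the sentence: "For any of the genes that demonstrate at least 2.5 fold increase (89% sensitivity calculated based on our preliminary data", the increase being in active disease compared with remission.

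The first two have no fold-change condition. No other section plans a correlation; section 10 contains only a power statement.

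**The concern.** The cut-off screens on a different quantity from the one the correlations measure. A fold change between two groups mixes the strength of the association, the spread of log expression, and the distance between the groups on DAS28. A gene with modest spread can track DAS28 closely and still differ by less than 2.5-fold. The condition also requires an increase, so a gene whose expression falls with activity cannot meet it however strong the relation.

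For a gene that misses, the plan holds no analysis of DAS28 as a continuous score and none of CRP, RF, anti-CCP or disease duration.

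The preliminary estimate comes from few donors, and sharpening it is one of the main things 200 donors could offer. The condition can withhold that gain. Nor does section 1 show that the cut-off will be met. Its fold change for blood-derived cells, "10 fold in RA peripheral blood (PB) in vitro differentiated macrophages compared to normal PB macrophages", compares RA with normal cells, not active disease with remission, and no fold change or correlation is given for IL-7.

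**Working it through.** **What the preliminary figures imply.** R² = 0.56 gives r = √0.56 = 0.748. Assuming a Pearson test, t = r√((n−2)/(1−r²)).

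- Monocytes, stated p = 8.4×10⁻⁵: n = 21 gives 9.6×10⁻⁵ and n = 22 gives 6.2×10⁻⁵, so about 21 or 22 donors. Fisher 95% CI for r at n = 21: 0.47 to 0.89.
- Macrophages, stated p = 2.4×10⁻⁶: n = 29 gives 3.0×10⁻⁶ and n = 30 gives 2.0×10⁻⁶, so about 29 or 30 donors. 95% CI about 0.53 to 0.87.
- The same r from 200 independent samples: 95% CI 0.68 to 0.80.

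**Model.** Inputs from section 2: 50 donors in remission and 150 not, cut-off 2.5-fold, log2(2.5) = 1.322. Assumptions: one sample and one readout per donor; log2 expression = SD × (r·z + √(1−r²)·e), with z the DAS28 score scaled to SD 1 and e independent standard normal; observed fold change from geometric means. The documents give neither the SD of log2 expression nor the DAS28 distribution, so both are varied.

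Gap in mean z between the groups:

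- One normal distribution cut at its 25th percentile: 0.3178/0.25 + 0.3178/0.75 = 1.695.
- Two normal clusters with within-group SD 0.6: √(1−0.36)/√(0.25×0.75) = 1.848.
- Two separated points, an extreme upper bound: 1/√(0.25×0.75) = 2.309.

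True log2 fold change = gap × r × SD. At r = 0.748 and SD 1.0 with one normal distribution: 1.695 × 0.748 × 1.0 = 1.268, a fold change of 2.41, just under the cut-off.

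SD at which the true fold change is exactly 2.5, from 1.322/(gap × r): at r = 0.748, 1.04 / 0.96 / 0.77 (normal / clusters / points).

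**Chance of passing, 20,000 simulated studies per cell, r = 0.748:**

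| SD of log2 expression | one normal | two clusters | two points |
|---|---|---|---|
| 0.6 | 0% | 0% | 0% |
| 0.75 | 0% | 0.1% | 38% |
| 1.0 | 34% | 68% | 100% |
| 1.25 | 95% | 99% | 100% |
| 1.5 | 99.9% | 100% | 100% |

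**Weaker-marker scenario, r = 0.50** (for example IL-7, for which no preliminary correlation is given):

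| SD of log2 expression | one normal | two clusters | two points |
|---|---|---|---|
| 0.75 | 0% | 0% | 0% |
| 1.0 | 0.1% | 0.4% | 12% |
| 1.25 | 8% | 19% | 75% |
| 1.5 | 41% | 61% | 98% |
| 2.0 | 90% | 96% | 100% |

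In every cell of both tables the correlation itself was significant (p < 0.05, n = 200) in at least 99.9% of simulated studies.

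**Several readouts.** Aim 1 names three cell preparations and section 2 two assays, so 3 × 2 = 6 readouts. Suppose any one of the six may qualify a gene, with an assumed residual correlation between readouts of 0.8 or 0.5. At r = 0.748 and SD 1.0, the pass rate rises from 34% to about 52% or 65% (one normal) and from 68% to about 84% or 91% (clusters). At SD 0.75 with one normal distribution it stays at 0%.

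**The case against.** The strongest reply is that the harm hangs on an SD that the documents do not supply. At the protocol's own R² the cut-off is almost always passed once the SD reaches 1.25, and nothing in the text favours a smaller value. This stands. A reader might infer from the low pass rates that the correlations will probably be lost; the documents do not support that, only that they can be.

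Second, the single-readout rates are one reading. Section 2 does not say which preparation, assay, group or visit supplies the fold change. If any readout counts, a gene passes more often near the cut-off. This also stands, and the working shows its size. It does not rescue a gene well below the cut-off.

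Third, the formal wording of Aim 1 asks whether levels are elevated, and the unconditional comparison and regression address that. This is fair: those results survive, and it would be wrong to infer that the main comparison is lost. But section 1 also places correlation with severity within aim 1, and a two-level disease status cannot answer that.

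Three further inferences should not be drawn. The IL-7R data do not make r = 0.50 an expected value: it sits near the lower limit of the monocyte interval and outside the macrophage one. The 89% sensitivity cannot be judged either way, because the data behind it are not in the documents. And inflation of the correlations that pass is too small to argue from: at r = 0.748 and SD 1.0 the mean among passing results is at most 0.769.

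**Conclusion.** The concern holds as a gap between the stated question and the planned reporting. Followed as written, the plan can leave a clearly correlated gene with no reported correlation, and will do so for any gene that falls with activity. At R² = 0.56 and one readout, the chance of meeting the cut-off runs from 0% at SD 0.6 to essentially 100% at SD 1.5, with the uncertain region around SD 0.75 to 1.0. These figures assume normal errors, a 50/150 split, one sample per donor and the three DAS28 shapes shown.

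What is at risk is limited to the correlation results; the active/inactive comparison, the regression and the data collection are unaffected. The change is worth making because it is cheap and because, with only two genes measured, the condition screens out almost nothing of use.

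**What to change.** Delete the 2.5-fold condition from Measure outcomes. Suggested wording:

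> For IL-7 and IL-7R, in each cell preparation and by each assay, the correlation of log expression with rheumatoid factor, anti-CCP, CRP, DAS28 and disease duration will be reported with a 95% confidence interval, whatever the fold change. One sample per donor will be used: the single sample from donors in remission on DMARDs and the onset sample from group 2. The fold change between active disease and remission will be reported separately with its 95% confidence interval. An increase of 2.5-fold or more will be noted descriptively and will not decide which correlations are calculated.

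The one-sample rule matters because group 2 gives blood at onset, 3 and 6 months. Pooling visits as if independent would invalidate the interval of 0.68 to 0.80. If later visits are to be used, the plan should name a method that accounts for repeated samples. It should also name the type of correlation coefficient.

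Cost: a few sentences, with no new patients, samples or assays. The downside is more coefficients: 2 genes × 5 variables = 10 for each preparation and assay, or up to 10 × 6 = 60. They should be presented as estimates with intervals, not as a set of significance tests.
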